15.6 Reporting and Exclusions

All of the participants with endpoint data will be included in the primary analysis. Participants are considered compliant for secondary “per protocol” statistical analysis if they have taken $\geq 80\%$ of their assigned study doses.

15.7 Evaluation of Toxicity

All participants will be evaluable for toxicity from the time of their first dose of apalutamide. Descriptive statistics of the type and frequency of all adverse events will be generated, including 95% confidence intervals.

A continuous monitoring rule for safety will be instituted, to guard against excess toxicity from pre-operative treatment with low dose apalutamide. Based on some pre-specified prior distribution for the unanticipated complication rate, the posterior distribution of the unanticipated complication rate will be derived and used to determine whether to stop the study early due to excessive complications.

Specifically, if the probability of the 10th percentile of the posterior distribution of the unanticipated complication rate $> 5\%$ is greater than 65% at a given time point, the study will be placed on hold to evaluate whether the unanticipated complications are related to apalutamide and referred to the UACC DSMB for evaluation of excess toxicity and recommendations on whether or not to stop the study early. We anticipate a low unanticipated complication rate for this study and, therefore, assume a beta distribution with parameters $a = 5$ and $b = 95$ (i.e. a mean complication rate of 5%) for the prior distribution. Below is a table summarizing the probability of the 10th percentile of the posterior probability of the unanticipated complication rate greater than 5% after 10 participants have been treated. If ≤ 3 participants have experienced any unanticipated complications, the probability that the 10th percentile of the posterior distribution $> 5\%$ is 0%. If 4 participants have experienced any unanticipated complications, the probability that the 10th percentile of the posterior distribution $> 5\%$ is 65.7%. If ≥ 5 participants have experienced any unanticipated complications, the probability that the 10th percentile of the posterior distribution $> 5\%$ is 100%.

Observed complication % (n = 10)	Assumed complication rate (prior)
	5% beta(5,95)
10% (i.e., 1 out of 10)	0%
20% (i.e., 2 out of 10)	0%
30% (i.e., 3 out of 10)	0%
40% (i.e., 4 out of 10)	65.7%
50% (i.e., 5 out of 10)	100%

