14.4 Data and Safety Monitoring Plan

The University of Arizona Cancer Center (UACC) Data and Safety Monitoring Board (DSMB) will provide oversight for subject safety for all UA CP-CTNet clinical trials consistent with the National Institutes of Health Policy for Data and Safety Monitoring dated June 10, 1998; further guidance statement issued by the NIH on June 5, 2000, and the policy for Data and Safety Monitoring by Data and Safety Monitoring Boards. The UACC DSMB meets quarterly.

Regular study-specific meetings will be used as a forum to review accrual rates, problematic issues relating to accrual and protocol implementation, adverse events occurrence, follow-up, and reporting; submission of all required study reports; and progress and outcomes of laboratory analyses.

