15. STATISTICAL CONSIDERATIONS

15.1 Study Design/Description

This is a Phase IIa open label dose-finding trial of low dose apalutamide in prostate cancer patients scheduled to undergo radical prostatectomy. The study is expected to include 2 dose groups. Up to 20 participants will be accrued into each dose group to initiate agent intervention.

The decision of dose de-escalation/escalation will be based on the PSA response. A participant with $\geq 25\%$ decline in serum PSA level is considered as a responder. For participants who do not complete the intervention and without post-intervention PSA value, we will conservatively assume the PSA decline to be $<25\%$, considered as a non-responder.

Accrued participants in the first dose cohort will receive apalutamide 60 mg MWF/wk for 4-8 weeks prior to radical prostatectomy. Based on the PSA response, an additional cohort of participants will receive a de-escalated dosing regimen at 60 mg once per week, or an escalated dosing regimen at 60 mg daily for 4-8 weeks prior to prostatectomy. To improve the efficiency of trial conduct, a continuous monitoring plan will be used for efficacy/futility evaluation after 12 participants have completed the dosing regimen. A PSA response rate of $\geq 50\%$ is considered sufficient for studying the 60 mg MWF/wk and the 60 mg daily dose in future active surveillance studies. The posterior probabilities of observing a response rate $\geq 50\%$ are summarized below based on the observed number of responders (N_r) and a non-informative prior for $N=12-20$ evaluable participants.

N_r	$N=12$	$N=13$	$N=14$	$N=15$	$N=16$	$N=17$	$N=18$	$N=19$	$N=20$
0	0.01	0.01	0.00	0.00	0.00	0.00	0.00	0.00	0.00
1	0.17	0.09	0.05	0.03	0.01	0.01	0.00	0.00	0.00
2	1.12	0.65	0.37	0.21	0.12	0.07	0.04	0.02	0.01
3	4.61	2.87	1.76	1.06	0.64	0.38	0.22	0.13	0.07
4	13.34	8.98	5.92	3.84	2.45	1.54	0.96	0.59	0.36
5	29.05	21.20	15.09	10.51	7.17	4.81	3.18	2.07	1.33
6	50.00	39.53	30.36	22.72	16.62	11.89	8.35	5.77	3.92
7	70.95	60.47	50.00	40.18	31.45	24.03	17.96	13.16	9.46
8	86.66	78.80	69.64	59.82	50.00	40.73	32.38	25.17	19.17
9	95.39	91.02	84.91	77.28	68.55	59.27	50.00	41.19	33.18
10	98.88	97.13	94.08	89.49	83.38	75.97	67.62	58.81	50.00
11	99.83	99.35	98.24	96.16	92.83	88.11	82.04	74.83	66.82
12	99.99	99.91	99.63	98.94	97.55	95.19	91.65	86.84	80.83
13	NA	99.99	99.95	99.79	99.36	98.46	96.82	94.23	90.54
14	NA	NA	100.00	99.97	99.88	99.62	99.04	97.93	96.08
15	NA	NA	NA	100.00	99.99	99.93	99.78	99.41	98.67

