16	NA	NA	NA	NA	100.00	99.99	99.96	99.87	99.64
17	NA	NA	NA	NA	NA	100.00	100.00	99.98	99.93
18	NA	NA	NA	NA	NA	NA	100.00	100.00	99.99
19	NA	100.00	100.00						
20	NA	100.00							

For the 60 mg MWF/wk dose, if the posterior probability is found to be $\geq 80\%$ at the evaluation (with the first evaluation starting after 12 evaluable participants), this dose cohort will be closed for efficacy and be de-escalated to 60 mg once a week schedule. If the posterior probability is found to be $\leq 20\%$ at the evaluation (with the first evaluation starting after 12 evaluable participants), this dose cohort will be closed for futility and be escalated to 60 mg daily dose. If the posterior probability is found to be $>20\%$

and <80%, the evaluation will be repeated with one additional evaluable participant, using the same criteria, up to a total of 20 evaluable participants.

If the regimen is escalated to 60 mg daily dose, the same probability criteria will be used to stop the dose cohort for efficacy or futility.

For the 60 mg once a week schedule, a PSA response rate of $\geq 25\%$ is considered sufficient for using this regimen as the starting regimen in future active surveillance studies.

The posterior probabilities of observing a response rate $\geq 25\%$ are summarized below based on the observed number of responders and a non-informative prior for 12-20 evaluable participants.

N_r	N=12	N=13	N=14	N=15	N=16	N=17	N=18	N=19	N=20
0	2.38	1.78	1.34	1.00	0.75	0.56	0.42	0.32	0.24
1	12.67	10.10	8.02	6.35	5.01	3.95	3.10	2.43	1.90
2	33.26	28.11	23.61	19.71	16.37	13.53	11.13	9.13	7.45
3	58.43	52.13	46.13	40.50	35.30	30.57	26.31	22.52	19.17
4	79.40	74.15	68.65	63.02	57.39	51.87	46.54	41.48	36.74
5	91.98	88.83	85.16	81.03	76.53	71.75	66.78	61.72	56.66
6	97.57	96.17	94.34	92.04	89.29	86.10	82.51	78.58	74.36
7	99.44	98.97	98.27	97.29	95.98	94.31	92.25	89.82	87.01
8	99.90	99.78	99.58	99.25	98.76	98.07	97.13	95.91	94.39
9	99.99	99.97	99.92	99.84	99.69	99.46	99.11	98.61	97.94
10	100.00	100.00	99.99	99.97	99.94	99.88	99.77	99.61	99.36
11	100.00	100.00	100.00	100.00	99.99	99.98	99.95	99.91	99.83
12	100.00	100.00	100.00	100.00	100.00	100.00	99.99	99.98	99.96
13	NA	100.00	100.00	100.00	100.00	100.00	100.00	100.00	99.99
14	NA	NA	100.00	100.00	100.00	100.00	100.00	100.00	100.00
15	NA	NA	NA	100.00	100.00	100.00	100.00	100.00	100.00
16	NA	NA	NA	NA	100.00	100.00	100.00	100.00	100.00
17	NA	NA	NA	NA	NA	100.00	100.00	100.00	100.00
18	NA	NA	NA	NA	NA	NA	100.00	100.00	100.00

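### The study-level safety rule in 15.7 most naturally pools both dose cohorts, so a clean first cohort raises the hold trigger at the daily dose; adding a within-cohort check would cost almost nothing

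*Combined protocol and SAP*

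**What the plan says.** Section 15.7 describes the safety rule at study level. The population is everyone dosed: "All participants will be evaluable for toxicity from the time of their first dose of apalutamide". The rate is a single one: "We anticipate a low unanticipated complication rate for this study". The prior is also single; the plan will "assume a beta distribution with parameters $a = 5$ and $b = 95$ (i.e. a mean complication rate of 5%) for the prior distribution". The criterion is that the 10th percentile of the posterior exceeds 5%, with a stated probability above 65%. The action is that "the study will be placed on hold to evaluate whether the unanticipated complications are related to apalutamide", with referral to the DSMB. Only the case of 10 treated participants is tabulated, where 4 events trigger a hold.

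Section 15.1 treats efficacy and futility differently, cohort by cohort. "The decision of dose de-escalation/escalation will be based on the PSA response". If the first regimen (60 mg Monday, Wednesday, Friday) meets the futility limit, "this dose cohort will be closed for futility and be escalated to 60 mg daily dose". The rule then restarts: "If the regimen is escalated to 60 mg daily dose, the same probability criteria will be used to stop the dose cohort". No matching statement is made for safety. The only dose-specific safety output is a descriptive adverse event table (15.5).

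**The concern.** The rule gives a boundary at every sample size, so it is not incomplete. The weakness concerns one branch of the design. The second cohort may receive 7 × 60 = 420 mg per week against 3 × 60 = 180 mg in the first (maintenance doses). Under pooling, 12 to 20 event-free men at the lower dose count as evidence that the higher dose is safe. The only numeric trigger for an excess complication rate then becomes slower just when the dose goes up. Escalation is decided on PSA response, so nothing in the escalation rule offsets this.

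**Working it through.** **Inputs.** Prior Beta(5,95) and the 10th-percentile criterion (15.7); first cohort of 12-20 evaluable participants and a second of up to 20 (15.1). Assumed: daily complication rates of 10%, 20% and 30%; first-cohort rate of 5% (the prior mean), varied to 2% and 10%.

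**Reproducing the plan's trigger.** With x events in n participants the posterior is Beta(5+x, 95+n−x). At n = 10 its 10th percentile is 4.32% for x = 3, 5.045% for x = 4 and 5.78% for x = 5. The smallest x above 5% is 4, as stated. For a given posterior the 10th percentile is a fixed number, so the plan's 65.7% looks like simulation output: estimating the percentile from 500 or 1,000 posterior draws puts it above 5% in 64.8% or 68.6% of runs at x = 4.

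**Boundary by total treated.** 4 of 11 gives 4.998% and 5 of 11 gives 5.73%; 5 of 26 gives 5.03% and 5 of 27 gives 4.99%; 6 of 40 gives 5.11%. So the trigger is 4 events at n = 4-10, 5 at 11-26 and 6 at 27-40.

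**Trigger at 10 daily participants.** The total is the first cohort plus 10. Subtract the first-cohort events from the boundary:

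| First-cohort events | First cohort 12-16 (total 22-26) | First cohort 17-20 (total 27-30) |
|---|---|---|
| 0 | 5 | 6 |
| 1 | 4 | 5 |
| 2 | 3 | 4 |
| Daily cohort alone | 4 | 4 |

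An event-free first cohort has probability 0.95^12 = 54% or 0.95^20 = 36% at a 5% rate.

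**Chance of a hold.** Let P_n(x) be the chance of x daily events after n daily participants with no hold yet. Then P_n(x) = (1−p)·P_{n−1}(x) + p·P_{n−1}(x−1), and any x at or above the boundary is removed as a hold. There is a look after every participant, and results are averaged over first-cohort counts at 5%, given no first-cohort hold. Each cell shows pooled only → either count:

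| Daily rate | By participant 10, first cohort 12 | By 10, first cohort 20 | By participant 20, first cohort 12 | By 20, first cohort 20 |
|---|---|---|---|---|
| 10% | 1.8% → 2.4% | 2.0% → 2.8% | 5.8% → 7.5% | 7.6% → 9.0% |
| 20% | 10% → 15% | 8% → 15% | 34% → 43% | 38% → 45% |
| 30% | 28% → 39% | 21% → 39% | 71% → 79% | 74% → 81% |

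- First cohorts of 13-19, by participant 20: the gain is 1.5-1.7 points at a 10% daily rate and 7-9 points at 20% or 30%.
- Event-free first cohort, 20% daily rate, by participant 20: 21.8% → 38.0% (first cohort 12) or 19.6% → 38.0% (20).
- First-cohort rate varied, 20% daily rate, by participant 20: at 2%, 27% → 39% for either size; at 10%, 46% → 51% (12) or 55% → 58% (20).

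**Cost.** With a true 5% rate in both cohorts, false holds during the second cohort go from 0.91% to 1.05% (first cohort 12) or from 1.45% to 1.58% (20).

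**Which first-cohort size is likely.** By the 15.1 table, futility can first be met at 4 of 12 (13.34), 5 of 14 (15.09), 6 of 16 (16.62), 7 of 18 (17.96) or 8 of 20 (19.17). At an assumed PSA response rate of 30%, escalation has probability 0.916, of which 0.724 falls at n = 12 (79%). At 40% the figures are 0.673 and 0.438 (65%). So 5 of 10 is the typical diluted trigger and 6 of 10 the extreme. The number treated may exceed the number evaluable, which is why the full 12-20 range is shown.

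**The case against.** The strongest objection is that pooling is inferred: 15.7 does not say what happens to the count when the second cohort opens. That is true, but the proposed rule helps under either reading. If the count restarts, detection at a 20% daily rate by participant 20 is 38.0%, and the either-count rule raises it to 42.8% (first cohort 12) or 45.3% (20).

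Second, pooling low doses of one drug is defensible and is not generally weaker. After 1 of 12 or 2 of 20 it is at least as sensitive as a restarted count. After 0 of 12 the two triggers also coincide, at 5, for daily participants 11-14. This stands, and it is why the pooled count should stay.

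Third, the edge at 5 of 26 is fragile. Simulating the percentile there gives about 63-66% against the 65% cut, so a first cohort of 16 could need 5 or 6 events. The effect is small.

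Fourth, other safeguards exist: dosing stops for related Grade 3-4 events (7.6), contact every 7-10 days (9.3), SAE contact within 24 hours (13.2.2), study meetings that review adverse events (14.4), and "The UACC DSMB meets quarterly". The daily dose is a quarter of the recommended 240 mg. The trial may also de-escalate, where the concern does not arise. Section 8.2 reports breast changes on the three-times-weekly regimen; if these count as unanticipated complications, which the plan does not define, the first cohort is not event-free. These points limit the importance of the concern without removing it.

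**Conclusion.** The concern holds as a modest, optional improvement. On the natural pooled reading, an event-free first cohort raises the trigger at 10 daily participants from 4 to 5 or 6. Averaged over first-cohort outcomes at 5%, checking both counts adds about 7-9 points to the chance of a hold by daily participant 20 at assumed daily rates of 20% or 30%, and under 2 points at 10%. The documents give no complication rate for the daily regimen, so these rates are assumptions. The point matters mainly on escalation after a clean first cohort.

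**What to change.** Keep the pooled count. Add to 15.7 that the same criterion is also evaluated on the current dose cohort alone, with the Beta(5,95) prior restarted when the second cohort opens, and that the study is held and referred to the DSMB if either count meets it. Add one table line with the cohort boundary: 4 events up to 10 participants, 5 events at 11-20.

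This takes one sentence and one table line, with no extra data or visits. The price is about 0.1 percentage point more false holds, each leading to DSMB review and not to automatic stopping. The change removes only the loss due to pooling. The prior still weighs as much as 100 participants, so with a 5% first-cohort rate a 20% daily rate is still missed more than half the time by participant 20.

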15.3 Sample Size

The study is expected to include 2 dose groups. Up to 20 eligible participants will be accrued into each dose group to initiate agent intervention. We anticipate accruing 1 participant every two months until all sites are activated. Once all sites are activated, we anticipate accruing 1-2 participants every month, we expect to complete the accrual of each dose cohort in 20 months.

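### Section 15.7: the 65.7% printed for 4 complications in 10 is not a value the stated safety model can give (the exact value is 100%), and the 65% cut-off is redundant

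*Combined protocol and SAP*

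**What the plan says.** Section 15.7 (Evaluation of Toxicity) introduces the rule thus: "A continuous monitoring rule for safety will be instituted, to guard against excess toxicity from pre-operative treatment with low dose apalutamide". Everyone treated counts: "All participants will be evaluable for toxicity from the time of their first dose of apalutamide". The prior for the unanticipated complication rate is Beta(5,95), with mean 5%. The monitored quantity is the 10th percentile of the posterior, compared with 5%. If the probability that this percentile exceeds 5% "is greater than 65% at a given time point, the study will be placed on hold", and the question goes to the DSMB.

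The section prints one worked case, described as "the probability of the 10th percentile of the posterior probability of the unanticipated complication rate greater than 5% after 10 participants have been treated". Text and table give 0% for 3 or fewer events, 65.7% for 4, and 100% for 5 or more. The sentence for 4 events reads: "If 4 participants have experienced any unanticipated complications, the probability that the 10th percentile of the posterior distribution" exceeds 5% is 65.7%. No other sample size is shown, and no simulation method is described.

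For efficacy and futility, section 15.1 says "a continuous monitoring plan will be used for efficacy/futility evaluation after 12 participants have completed the dosing regimen", and it prints the posterior probabilities for every n from 12 to 20. On size, section 15.3 says: "Up to 20 eligible participants will be accrued into each dose group to initiate agent intervention". Two groups are expected, so up to 2 × 20 = 40 participants may be treated.

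**The concern.** A percentile of a known distribution is not random. Once the prior is fixed and the events are counted, the posterior is fully known, and its 10th percentile either exceeds 5% or does not. No intermediate probability exists, so 65.7% cannot come from the model as stated.

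This matters because of where the figure sits. It is in the plan's quantitative safety hold, at the one printed count where the decision turns, and it clears the 65% cut-off by only 65.7 − 65 = 0.7 percentage points. A reader would take 4 of 10 to be a close call against 65%. If the number came from random draws, a re-run could fall on the other side of the cut-off with the same data.

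**Working it through.** **Inputs (section 15.7).** Prior Beta(5,95); 10th percentile; limit 5%; hold cut-off 65%; printed case n=10. The range to n=40 comes from section 15.3.

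**Formula.** After x events in n participants the posterior is Beta(5+x, 95+n−x). Call its 10th percentile q. Then q > 5% exactly when P(rate ≤ 5% | data) < 0.10, that is, when P(rate > 5% | data) > 0.90.

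**Step 1: try to reproduce the printed column at n=10.**

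| Events x | Posterior | q | P(rate > 5%) | Exact P(q > 5%) | Printed |
|---|---|---|---|---|---|
| 1 | Beta(6,104) | 2.92% | 53.6% | 0% | 0% |
| 2 | Beta(7,103) | 3.61% | 69.6% | 0% | 0% |
| 3 | Beta(8,102) | 4.32% | 82.1% | 0% | 0% |
| 4 | Beta(9,101) | 5.045% | 90.4% | 100% | 65.7% |
| 5 | Beta(10,100) | 5.78% | 95.3% | 100% | 100% |

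Four of the five cells reproduce. The cell at 4 of 10 does not. Nor is 65.7% the posterior probability that the rate exceeds 5%, which is 90.4% there. A mis-updated posterior, Beta(9,105), gives 88.7% for that probability, and a flat prior gives 99.99%.

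**Step 2: a possible origin.** Suppose q is estimated from M random draws of the posterior. At 4 of 10, each draw falls at or below 5% with probability 1 − 0.904 = 0.096. The estimate exceeds 5% when fewer than about 0.1M draws do so, which is a binomial probability. Depending on how the sample percentile is defined, this gives:

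- M=500: 59.7% to 65.4%
- M=1,000: 65.1% to 68.9%
- M=2,000: 71.8% to 74.2%
- M=10,000: 90.9% to 91.5%
- M=100,000: 100%

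At 3 and 5 of 10 the result stays at 0% and 100% for M of 500 or more. The whole printed column is therefore consistent with roughly 500 to 1,000 draws. This is an inference, because the documents state no draw count.

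**Step 3: the limit at other sample sizes.** The smallest x with q > 5%:

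| n | Events needed for a hold |
|---|---|
| 1–3 | not reachable |
| 4–10 | 4 |
| 11–26 | 5 |
| 27–40 | 6 |

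Values of q at the edges: 3/3 gives 4.62%, 4/4 gives 5.34%, 4/10 gives 5.045%, 4/11 gives 4.998%, 5/26 gives 5.034%, 5/27 gives 4.994%, and 6/40 gives 5.107%.

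**Step 4: sensitivity if the rule is simulated.** At 5/26, P(rate > 5%) is 90.3%, so the exact rule holds. With 500 draws the simulated figure is about 63%, below 65%, which means no hold. With 10,000 draws the binomial formula of step 2 gives about 87%, which means a hold. The same data could therefore give opposite decisions.

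**The case against.** The strongest reply is that nothing in practice goes wrong. All five printed decisions at n=10 are right. A probability of 0 or 1 can still be compared with 65%, so the rule runs as written at every n: hold when the percentile exceeds 5%. Section 15.7 supplies every input, and a formula with one worked example specifies a rule. A hold leads to an evaluation of relatedness and DSMB review, not automatic stopping. Adverse events are also monitored regularly (section 15.9), and the DSMB meets quarterly (section 14.4).

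Most of this stands. A reader might infer that the rule cannot be operated away from n=10, or that the 65% cut-off makes it unusable. The documents do not support either. The limits are unstated rather than undefined, and the cut-off is superfluous under exact evaluation, because any value from 0% to just below 100% gives the same decisions.

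A reader might also suspect that the intended rule is P(rate > 5%) above 65%, which would hold at 2 of 10 (69.6%). The text and table rule that out: they show 0% at 2 and at 3 of 10, and the 10th percentile is named throughout.

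What the reply does not answer is that one printed figure is wrong, and that it is printed against the rule's own cut-off. The layer that produced it invites a simulated implementation, in which borderline outcomes depend on computing choices.

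**Conclusion.** The point holds as an error of calculation and expression. The 65.7% at 4 of 10 should be 100%, and the 65% layer is redundant under exact evaluation. The decisions at n=10 do not change, and the rule can be run at any n from the inputs given. A continuous rule is tabulated at one sample size only, whereas its efficacy counterpart is tabulated from 12 to 20. That is an omission of convenience, not a gap in the definition.

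The practical exposure is limited to borderline counts such as 4/10 and 5/26, and it arises only if the percentile is estimated from a modest number of random draws. That condition is inferred from the printed figure and not stated in the plan. The exact results rest on the Beta(5,95) prior and the usual conjugate update. The limits up to n=40 also assume that events are pooled across dose groups, which is how the study-level wording of section 15.7 reads, and n=40 is reached only if both cohorts fill.

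**What to change.** In section 15.7:

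1. State the rule as: hold if the 10th percentile of Beta(5+x, 95+n−x) exceeds 5%, equivalently if P(rate > 5% | data) > 0.90, computed exactly.
2. Delete the 65% layer.
3. Replace the 0% / 65.7% / 100% column and the matching sentences with the exact percentiles (2.92%, 3.61%, 4.32%, 5.045% and 5.78% for 1 to 5 events in 10) or with P(rate > 5%).
4. Print the implied limit: none for n=1–3, 4 events for n=4–10, 5 for n=11–26, 6 for n=27–40. Confirm that events are pooled across dose groups.

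The cost is a few sentences and one table. The prior, the percentile, the 5% limit, the sample size, the schedule and the printed n=10 decisions all stay as they are.
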